4.5.8 Electrocardiograms

Single ECG recordings will be obtained at specified timepoints, as outlined in the schedule of activities (see [Appendix 1](#)), and may be obtained at unscheduled timepoints as indicated.

All ECG recordings must be performed using a standard high-quality, high-fidelity digital electrocardiograph machine equipped with computer-based interval measurements. Lead placement should be as consistent as possible. ECG recordings must be performed after the patient has been resting in a supine position for at least 10 minutes.

All ECGs are to be obtained prior to other procedures scheduled at that same time (e.g., vital sign measurements, blood draws) and should not be obtained within 3 hours after any meal. Circumstances that may induce changes in heart rate, including environmental distractions (e.g., television, radio, conversation) should be avoided during the pre-ECG resting period and during ECG recording.

For safety monitoring purposes, the investigator must review, sign, and date all ECG tracings. Paper copies of ECG tracings will be kept as part of the patient's permanent study file at the site. Digital recordings will be stored at site. The following should be recorded in the appropriate eCRF: heart rate, RR interval, QRS interval, PR duration, uncorrected QT interval, and QT interval corrected through use of Fridericia's formula (QTcF) based on the machine readings of the individual ECG tracings. Any morphologic waveform changes or other ECG abnormalities must be documented on the eCRF. If considered appropriate by the Sponsor, ECGs may be analyzed retrospectively at a central laboratory.

If at a particular postdose timepoint the mean QTcF is > 500 ms and/or > 60 ms longer than the baseline value, another ECG must be recorded, ideally within the next 5 minutes, and ECG monitoring should continue until QTcF has stabilized on two successive ECGs. The Medical Monitor should be notified. SOC treatment may be instituted per the discretion of the investigator. If a PK sample is not scheduled for that timepoint, an unscheduled PK sample should be obtained. A decision on study drug discontinuation should be made, as described in Section 5.1.3.2. The investigator should also evaluate the patient for potential concurrent risk factors (e.g., electrolyte abnormalities, co-medications known to prolong the QT interval, severe bradycardia).

4.5.9 Patient-Reported Outcomes

4.5.9.1 EORTC QLQ-C30 Background

The EORTC QLQ-C30 (see [Appendix 5](#)) is a validated and reliable self-reported measure (Aaronson et al. 1993; Sprangers et al. 1996; Fitzsimmons et al. 1999) consisting of 30 questions that assess 5 aspects of patient functioning (physical, emotional, role, cognitive, and social), 8 symptoms (fatigue, nausea and vomiting, pain, dyspnea, insomnia, appetite loss, constipation, and diarrhea), financial difficulties, and GHS/HRQoL with a recall period of the previous week. The EORTC QLQ-C30 data will be scored according to the EORTC scoring manual (Fayers et al. 2002). Scale scores will be obtained for each of the multi-item and single-items scales by using a linear transformation for standardization of the calculated raw score. The EORTC QLQ-C30 takes approximately 10 minutes to complete.

To fully characterize venetoclax with fulvestrant compared with single-agent fulvestrant as a second-line treatment in patients with MBC, PRO data will be collected using the EORTC QLQ-C30. Specifically, the GHS/overall HRQoL scale score (Questions 29 and 30) will be used to assess patients' overall HRQoL and the pain (Questions 9 and 19)

scale of the EORTC QLQ-C30 will be used evaluate the proportion of patients with disease-related pain of venetoclax+fulvestrant compared with fulvestrant alone.

The EORTC QLQ-C30 will be administered to patients to assess pain, disease/treatment-related symptoms, functioning, and HRQoL (see Section 4.5.9.2 and Appendix 5).

4.5.9.2 EORTC QLQ-C30 Procedures

The EORTC-QLQ-C30 must be administered at the pre-specified clinic visits, and the questionnaire must be completed by the patient at the investigational site at the start of the clinic visit prior to receiving information on disease status, prior to any other study assessments, and before administration of study treatment. Patients will complete paper versions of the questionnaire, which will be provided by site staff. Interviewer assessment is allowed but can only be conducted by a member of the clinic staff for patients who are unable to complete the measures on their own. Study personnel should review all questionnaires for completeness before the patient leaves the investigational site. Appropriate translated versions of the local language of the PRO measures will be available at the site.

4.5.10 Optional Tumor Biopsies

Consenting patients will undergo optional tumor biopsies at Cycle 3 Day 1 (± 3 days) after treatment initiation and at disease progression and may undergo additional on-treatment biopsies at any other time at the investigator's discretion (if deemed clinically feasible by the investigator). Where fresh biopsy is possible, samples collected via resection, core-needle biopsy, or excisional, incisional, punch, or forceps biopsy are acceptable. (Note: biopsies collected via fine-needle aspirations are not acceptable.) For sampling procedures, storage conditions, and shipment instructions, see the laboratory manual.

The Informed Consent Form will contain a separate section that addresses optional biopsies. A separate, specific signature will be required to document a patient's agreement to undergo optional biopsies. The investigator should document whether or not the patient has given consent to participate and (if applicable) the date(s) of consent, by completing the Optional Biopsy Sample Informed Consent eCRF. Samples may be used for exploratory biomarker research as described in Section 4.5.7.

4.6 TREATMENT, PATIENT, STUDY, AND SITE DISCONTINUATION

4.6.1 Study Treatment Discontinuation

Patients must permanently discontinue study treatment if they experience any of the following:

- Any medical condition that the investigator or Sponsor determines may jeopardize the patient's safety if he or she continues to receive study treatment

- Investigator or Sponsor determines it is in the best interest of the patient (including high-grade toxicities when continuing treatment is deemed detrimental)
- Pregnancy
- Use of an anti-cancer therapy not required per protocol
- Disease progression

The primary reason for study treatment discontinuation should be documented on the appropriate eCRF. Patients who discontinue study treatment prematurely will not be replaced.

Patients will return to the clinic for a treatment completion or treatment discontinuation visit 28 days (+3 days) after the last dose of study drug (see [Appendix 1](#) for additional details).

After treatment discontinuation due to disease progression, information on survival follow-up and new anti-cancer therapy will be collected via telephone calls, patient medical records, and/or clinic visits approximately every *3 months, or more frequently*, until death, loss to follow-up, withdrawal of consent, or study termination by the Sponsor, whichever occurs first.

Patients who are discontinued from study treatment for reasons other than disease progression and have started follow-on treatment/s will be followed for survival approximately every *3 months, or more frequently*, until death, lost to follow-up, withdrawal of consent, or study termination by the Sponsor, whichever occurs first.

Patients who are discontinued from study treatment/s for reasons other than disease progression and have not started follow-on treatment/s will be followed for disease status every 8 weeks (± 5 days) from the date of randomization until Week 24 (± 5) days and every 12 weeks (± 5 days), thereafter, until disease progression, loss to follow-up, withdrawal of consent, death or study termination by the Sponsor, whichever occurs first (see [Appendix 1](#) for additional details).

4.6.2 Patient Discontinuation from Study

Patients have the right to voluntarily withdraw from the study at any time for any reason. In addition, the investigator has the right to withdraw a patient from the study at any time. Reasons for withdrawal from the study may include, but are not limited to, the following:

- Patient withdrawal of consent
- Study termination or site closure
- Patient non-compliance, defined as failure to comply with protocol requirements as determined by the investigator or Sponsor

Every effort should be made to obtain information on patients who withdraw from the study. The primary reason for withdrawal from the study should be documented on the

appropriate eCRF. If a patient requests to be withdrawn from the study, this request must be documented in the source documents and signed by the investigator. Patients who withdraw from the study will not be replaced.

If a patient withdraws from the study, the study staff may use a public information source (e.g., county records) to obtain information about survival status.

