4.3.2.1 Venetoclax

Study patients will self-administer venetoclax tablets by mouth daily. Venetoclax is formulated as 100-mg tablets, so patients will take eight 100-mg tablets QD to receive an 800-mg dose. Each dose of venetoclax will be taken with approximately 240 mL of water within 30 minutes after the patient's first meal of the day (e.g., breakfast).

On days that predose pharmacokinetic (PK) sampling is required, the patient's first meal of the day (e.g., breakfast) will be provided in the morning at the clinic, and venetoclax dosing will occur in the clinic after completion of the meal to facilitate PK sampling.

On days when both venetoclax and fulvestrant are given, the order of study treatment administration will be venetoclax followed by fulvestrant (there is no minimum time required between the administration of venetoclax and the start of fulvestrant administration). If vomiting occurs within 15 minutes of taking venetoclax and all expelled tablets are still intact, another dose may be given and the second dose noted in the drug log. Otherwise, no replacement dose is to be given. In cases where a dose of venetoclax is missed or forgotten, the patient should take the dose as soon as possible, ensuring that the dose is taken within 8 hours of the missed dose with food. Otherwise, the dose should not be taken. On days when patients are scheduled to have blood samples collected for PK assessments, the time of each dose of venetoclax will be recorded to the nearest minute. Venetoclax must be stored according to labeled storage conditions. There is to be no break between cycles.

As of 8 October 2020, all active patients in the venetoclax plus fulvestrant arm of the study will be requested to discontinue the venetoclax treatment immediately, and will be given the option to continue fulvestrant treatment alone.

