4.3.2.2 Fulvestrant

Fulvestrant 500 mg will be administered in the clinic as two 250-mg IM injections on Cycle 1 Days 1 and 15 and then on Day 1 of each subsequent 28-day cycle. For details regarding the dosing instructions and safety profile of fulvestrant, refer to the local fulvestrant package insert or Summary of Product Characteristics.

The fulvestrant dose level cannot be modified. In general, the investigator may consider continuing fulvestrant if the adverse event observed is not thought to be fulvestrant-related. See Section 5.1.3 for guidelines for treatment interruption or discontinuation of fulvestrant.

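### Section 4.6.2 lets the investigator end a consenting patient's study participation, including for non-compliance, although Sections 3.1 and 4.6.1 give no such reason for stopping scans or survival follow-up.

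*Combined protocol and SAP*

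**What the plan says.** **Withdrawal from the study (Section 4.6.2).** The section states that "the investigator has the right to withdraw a patient from the study at any time". It introduces its list with "Reasons for withdrawal from the study may include, but are not limited to, the following", so the list is permissive and open. Withdrawal of consent is one entry. A separate entry is "Patient non-compliance, defined as failure to comply with protocol requirements as determined by the investigator or Sponsor". The section also asks for every effort to obtain information on patients who withdraw, and allows, without requiring, a public-records check of survival status.

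**Stopping treatment (Section 4.6.1).** The list opens with "Patients must permanently discontinue study treatment if they experience any of the following" and has five entries: a medical condition that puts safety at risk, the patient's best interest, pregnancy, other anti-cancer therapy, and progression. Non-compliance is not named.

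**Follow-up after stopping treatment (Sections 3.1 and 4.6.1).** Patients who stop without progression and without new therapy stay on the scan schedule, "thereafter, until disease progression, loss to follow-up, withdrawal of consent, death or study termination by the Sponsor, whichever occurs first". Those who have started new therapy are followed for survival about every 3 months, "until death, lost to follow-up, withdrawal of consent, or study termination by the Sponsor, whichever occurs first". Patients who have progressed have the same survival contact.

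**Treatment by arm.** For the experimental drug, "Study patients will self-administer venetoclax tablets by mouth daily" (Section 4.3.2.1). For the drug common to both arms, "Fulvestrant 500 mg will be administered in the clinic" (Section 4.3.2.2). The study is open-label (Section 3.1).

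**Analysis.** The ITT population is all randomized patients (Section 6). PFS is censored at the last tumor assessment (6.4.2.1) and OS at the last date known alive (6.4.2.4). For CBR, a non-responder rule is stated only for patients with no response assessment at all (6.4.1).

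**The concern.** Non-compliance with treatment is a reason to ask whether a patient should stay on treatment. It is not in itself a reason to stop observing her. Section 4.6.2 does not separate the two, so a patient who still consents to scans and telephone contact can leave both because of a judgement by the investigator or Sponsor.

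Two features make the loss potentially related to arm. The person deciding knows the assignment. Also, adherence to daily tablets, with the food and CYP3A restrictions of Sections 4.4.2.1 and 4.4.3, is a requirement that only the venetoclax arm could fail. If the reasons for non-adherence are related to prognosis, censoring at withdrawal is informative. The documents show neither that this happened nor that it did not.

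At stake are the Week 24 status that defines stable disease as clinical benefit, the PFS event date, and the date of death. OS matters most now. Section 1.4 calls it immature, with a 27.2% event-to-patient ratio and median survival follow-up of 9.89 months, and Version 4 moved survival contact from about every 6 months to about every 3 months.

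**Working it through.** **1. The end points of follow-up, side by side**

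| Event | Ends scans or survival follow-up under 3.1 / 4.6.1? | Ground for leaving the study under 4.6.2? |
|---|---|---|
| Withdrawal of consent | yes | yes |
| Study termination | yes | yes |
| Progression | scans only | not listed |
| Non-compliance, as judged | no | yes |
| Other investigator decision | no | yes (at any time) |

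The last two rows are the conflict. Deleting the non-compliance entry alone would not remove it, because the general power in the last row remains.

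**2. Consequence for a patient withdrawn before Week 24 with stable disease**
- CBR: she has scans, so the no-assessment rule does not apply to her. Without a Week 24 scan she cannot show stable disease of 24 weeks, but she stays in the ITT denominator.
- PFS: censored at her last scan.
- OS: censored when last known alive, unless the effort clause or a records check yields a later date.

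**3. The plan's own precision figure (Section 6.1)**

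Inputs: 50 per arm, CBR 40% and 60%, 80% CI.
- SE = sqrt(0.4×0.6/50 + 0.6×0.4/50) = 0.0980.
- Half-width = 1.2816 × 0.0980 = 12.6 points, giving 7.4% to 32.6%.
- Adding a continuity correction of (1/50 + 1/50)/2 = 2.0 points gives 14.6 points, or 5.4% to 34.6%. This rounds to the stated 15% and 5% to 35%.

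The present point does not change that figure.

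**4. What lost Week 24 data could do to CBR**

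Arm sizes follow from Section 1.4: 19 deaths at 37.3% gives 51, 9 at 17.3% gives 52, and 51 + 52 = 103. One venetoclax patient is 1/51 = 2.0 points, two are 3.9 and three are 5.9. These are maxima: the shift is zero for a patient who would not have had clinical benefit.

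Illustration on design values, because no rate is given: *k* of 50 venetoclax patients are withdrawn early and counted as no benefit, and 60% of them would have had benefit. The observed rate is 0.60 × (50 − k)/50, and the limits are uncorrected.

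| k | CBR difference | 80% lower limit |
|---|---|---|
| 0 | 20.0 | 7.4 |
| 2 | 17.6 | 5.0 |
| 5 | 14.0 | 1.3 |
| 8 | 10.4 | −2.3 |

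**5. Direction for OS**

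Recorded deaths are 19/51 = 37.3% and 9/52 = 17.3%, a difference of 19.9 points. If one, two or three venetoclax-arm deaths had gone unrecorded, the true proportion would be 20/51 = 39.2%, 21/51 = 41.2% or 22/51 = 43.1%. Missed deaths in that arm would therefore mean that the recorded excess is too small.

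**The case against.** The sponsor has a fair reply, and much of it stands.

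- **The rule is permissive and has safeguards.** Nobody has to be withdrawn, and Section 4.6.2 asks for every effort to obtain information. This softens the loss for OS. It does not restore scans, and it sets no contact schedule.
- **It is largely overtaken by events.** The tablet mechanism ended on 8 October 2020, and rewording cannot alter the reported CBR. This stands, and confines the point mainly to continuing survival follow-up.
- **Off-treatment deaths were being captured.** Section 1.4 reports 17 + 9 = 26 of 28 deaths more than 28 days after the last dose. That is reassuring in general, but says nothing about patients withdrawn from the study.

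A reader might also infer more than the documents support:

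- *That withdrawn patients leave the ITT analysis.* They do not. Sections 6 and 6.4 keep every randomized patient in the assigned arm. The harm is missing outcomes.
- *That non-compliance can arise in one arm only.* The definition covers any protocol requirement, so missed visits, scans or injections count in both arms. Only tablet non-adherence is confined to venetoclax.
- *That patients who stop tablets for toxicity will be labelled non-compliant.* Sections 5.1.3.2 and 5.1.3.3 give toxicity its own handling. Patients who stop after a long toxicity-related interruption are still followed for progression.
- *That study withdrawal is the only route for a non-compliant patient.* Section 4.6.1 is not stated to be exhaustive and has a broad best-interest ground.
- *That the reported OS hazard ratio of 2.56 (95% CI 1.11 to 5.89) is in doubt, or that a few deaths would carry its interval across 1.* Removing deaths that were recorded describes another data set. Nothing in the documents says that any death was missed.

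**Conclusion.** The conflict between Section 4.6.2 and Sections 3.1 and 4.6.1 is real and rests on the text alone. It permits an avoidable, arm-aware loss of outcome data that the effort clause and the optional records check only partly offset.

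Its actual size is unknown. The bound is 2.0 CBR points per withdrawn venetoclax patient; the larger shifts tabulated above depend on an assumed number of withdrawals and an assumed 60% benefit rate among them. For OS, only the direction can be stated: unrecorded venetoclax-arm deaths would understate the signal.

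The point does not challenge the primary analysis or the analysis set. It is worth acting on because survival follow-up continues. On the plan's own timing, a primary analysis 6 months after the last patient entered and a study end 2 years after the last enrollment leave 24 − 6 = 18 months of follow-up, assuming that the 6-month trigger applied and the study is not ended sooner.

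**What to change.** 1. Reconcile Section 4.6.2 with Sections 3.1 and 4.6.1 by stating that neither non-compliance nor any investigator or Sponsor decision about an individual patient ends scan or survival follow-up while her consent stands. This also covers the general power to withdraw at any time.
2. When a patient withdraws, record separately whether she withdraws from treatment, from visits and scans, or from survival contact.
3. For patients already withdrawn without withdrawal of consent, seek vital status, where local law allows, in time for the next OS analysis, and report their number by arm.

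Whether non-compliance should stop treatment is a clinical matter for the sponsor. This change does not require it to be added to the treatment-stopping list in Section 4.6.1.

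Cost: a wording change, one eCRF field, and a few more patients kept on the existing 8/12-weekly scan or 3-monthly survival schedule. No new procedure and no change in sample size.

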4.6.3 Study Discontinuation

The Sponsor has the right to terminate this study at any time. Reasons for terminating the study may include, but are not limited to, the following:

- The incidence or severity of adverse events in this or other studies indicates a potential health hazard to patients
- Patient enrollment is unsatisfactory

The Sponsor will notify the investigator if the Sponsor decides to discontinue the study.

4.6.4 Site Discontinuation

The Sponsor has the right to close a site at any time. Reasons for closing a site may include, but are not limited to, the following:

- Excessively slow recruitment
- Poor protocol adherence
- Inaccurate or incomplete data recording
- Non-compliance with the International Council for Harmonisation (ICH) guideline for Good Clinical Practice
- No study activity (i.e., all patients have completed the study and all obligations have been fulfilled)

5. ASSESSMENT OF SAFETY

5.1 SAFETY PLAN

Venetoclax was granted approval in the United States (see Venclaxta[®] U.S. Prescribing Information 2016) and conditional market approval by the EMA (see Venclyxto[®] EMA Summary of Product Characteristics 2016) as monotherapy for the treatment of patients with CLL who have 17p deletion.

Venetoclax, however, is not approved for the treatment of breast cancer, and clinical development is ongoing. The safety plan for patients in this study is based on clinical experience with venetoclax in completed and ongoing studies. The anticipated important safety risks for venetoclax are outlined below. Please refer to the Venetoclax Investigator's Brochure for a complete summary of safety information.

Several measures will be taken to ensure the safety of patients participating in this study. Eligibility criteria have been designed to exclude patients at higher risk for

toxicities. Patients will undergo safety monitoring during the study, including assessment of the nature, frequency, and severity of adverse events. In addition, guidelines for managing adverse events, including criteria for dosage modification and treatment interruption or discontinuation, are provided below.

5.1.1 Risks Associated with Venetoclax

Clinical experience gained thus far with venetoclax has demonstrated that it is generally well tolerated, and toxicities appear to be mostly manageable and/or reversible; see the Venetoclax Investigator's Brochure for more information. On the basis of clinical data to date, the following known and potential risks with venetoclax are described below.

Guidelines around the management of these risks through dose and schedule modifications are described in Section [5.1.3](#).

